## 7.6 Supportive Analyses of the Secondary Outcome Measures

Acknowledging that individuals may vary in presence and types of SUD diagnoses, additional supportive analyses will be done to evaluate the differing numbers of steps achieved along the modified SUD Cascade of Care for each sub-group of enrolled participants: primary OUD, primary SUD other than OUD, and no identified SUD at baseline (as determined via administration of the DSM-5 checklist). These subgroup analyses will utilize the same Poisson regression model as for the prespecified secondary outcome analysis, but with the inclusion of an interaction term between treatment and subgroup. Contrasts will be used to test for statistically significant differences in the secondary outcome (number of steps achieved) by subgroup.

## 7.7 Definition of the Exploratory Outcome Measures

1. Exploratory Aim 1: To assess the effects of PILOT versus TAU on the achievement (yes/no) and magnitude of achievement (e.g., improvement in Addiction Recovery Capital Scale by 3 points, number of steps achieved) on the modified SUD Cascade of Care.
2. Exploratory Aim 2: To evaluate the effectiveness of PILOT versus TAU on initiation of MOUD in the ED (EDM) for those with any level of OUD at baseline (DSM; assessed via self-report upon ED discharge or in follow-up assessment if unable to be assessed at ED discharge).
3. Exploratory Aim 3: To assess the effects of PILOT versus TAU on substance use frequency at 30, 90, and 180 days via self-reported days of illicit opioid use measured by Timeline Follow-Back (TLFB).
4. Exploratory Aim 4: To evaluate the degree of engagement in Peer Support Services in those randomized to PILOT versus TAU at 30, 90, and 180 days, measured as the number of contacts received or initiated with a Peer Support Specialist in the past month (PIL; phone, video, or in-person).

5. Exploratory Aim 5: To evaluate the effectiveness of PILOT versus TAU on self-reported attendance in 12-step meetings, peer support services, other recognized recovery organization, or formal SUD treatment at any time point during enrollment, defined as self-report of having attended a meeting or appointment (SAA; phone, video, or in-person).
6. Exploratory Aim 6: To evaluate the effectiveness of PILOT versus TAU on the percentage of urine toxicology screens (UDT) positive for primary substance of use (as per DSM-5 Checklist: opioids, alcohol, amphetamines, cannabis, cocaine, or sedatives) at 30-, 90-, 180-, and 210-days post-randomization.
7. Exploratory Aim 7: To evaluate the effectiveness of PILOT versus TAU on repeat non-fatal overdose (ODI) and 210-day rates of death (DTH; all-cause mortality), including death by overdose.

## 7.8 Analyses of the Exploratory Outcome Measures

The following are the planned statistical analysis methods for the specified exploratory objectives. However, given the exploratory nature of these, the actual analysis methods may differ from the proposed methods given below.

1. Each step on the modified SUD Cascade of Care will be treated as a binary outcome. A separate logistic regression model will be fit to each with at least a treatment covariate. The effect of PILOT as compared to TAU will be measured by an odds ratio (OR). The OR will be reported, along with 95% confidence interval and p-value, for each step. This process will be repeated for the 30-, 90-, and 180-day outcomes.
2. Initiation for medications for OUD in the ED, among those participants with OUD, will be summarized by frequencies and percentages in each treatment arm. The effect of PILOT compared to TAU will be measured by an OR with 95% confidence interval. A Chi-squared test will be performed.
3. Number of days of self-reported frequency of use in the past 7 days will be summarized by treatment arm. A hypothesis test analogous to the primary outcome will be conducted.
4. The number of meaningful contacts with a PILOT peer in the past month will be summarized by treatment arm. Similar to the primary outcome, the effect will be measured by a RR with 95% confidence interval. A hypothesis test analogous to the primary outcome will be conducted.
5. Self-reported attendance in a 12-step meeting, peer support services, other recognized recovery organization, or formal SUD treatment at any time during study participation will be summarized by frequency and percentages in each treatment arm. The effect of PILOT as compared to TAU will be measured by an OR with 95% confidence interval. A Chi-squared test will be performed.
6. The percent of urine toxicology screens positive for primary substance of use will be summarized by proportion greater than 0% and continuous descriptive statistics for the proportion positive by treatment arm.
7. Occurrence of a non-fatal overdose at any time during study participations will be summarized by frequencies and percentages. The effect of PILOT as compared to TAU will be measured by an OR with 95% confidence interval. A Chi-squared test will be

performed. The same process will be done for all-cause mortality and death by overdose. In the event of likely dropout, time-to-event analyses may need to be performed instead. In such cases, simple Kaplan-Meier plots will be given with associated log-rank tests on the effect of PILOT as compared to TAU. Cox proportional hazards regression models may be considered as well. All-cause mortality or death by overdose may present a competing risk for non-fatal overdose. Causes of death different from overdose (that is, those with an all-cause mortality that are not overdose) may present a competing risk for death by overdose as well. As such, appropriate Fine and Gray models will be considered.

The exploratory objectives will be tested as applicable, with two-sided tests and with a type I error rate of 0.05. No attempt will be made to adjust for multiple comparisons within the exploratory objectives.

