## 2.0 SUMMARY OF STUDY DESIGN AND PROCEDURES

### 2.1 Study Objectives

The primary objective of this study is to advance understanding and improve outcomes for individuals who present to an Emergency Department (ED) after surviving a non-fatal overdose involving opioids (NFOO). To achieve this objective, the study will evaluate the preliminary effectiveness of a specialized, enhanced peer recovery intervention tailored for NFOO survivors, called Peer Intervention to Link Overdose Survivors to Treatment (PILOT), on self-reported overdose risk behaviors for individuals who present to the ED after a NFOO. The PILOT intervention will be compared to treatment as usual (TAU) in the ED setting. The secondary objectives of the study are to: 1) evaluate the number of steps achieved along a modified Substance Use Disorder (SUD) Cascade of Care for individuals randomized to PILOT versus TAU, and 2) to assess whether NFOO survivors within an ED setting are willing to engage with overdose peer support using the PILOT model (feasibility).

Exploratory objectives are to assess the effects of PILOT versus TAU on the magnitude of achievement on the modified SUD Cascade of Care, on initiation of Medication for Opioid Use Disorder (MOUD), on substance use frequency, on engagement in Peer Support Services, on self-reported attendance at a recognized recovery organization or formal SUD treatment, on the percentage of toxicology screens positive for primary substance use, and on repeat non-fatal overdose and rates of death (see Section 7.7).

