## **2.2 Study Design and Procedures**

### **2.2.1 Study Design**

This is an unblinded two-arm, multi-site, prospective, randomized controlled pilot trial comparing the effectiveness of the PILOT intervention with TAU on the frequency of self-reported overdose risk behaviors for those who survive a NFOO and present to the ED.

A total of approximately 150 eligible patients will be randomized (approximately 50 per each of 3 sites) in a 1:1 ratio to either TAU or PILOT over 12 months of recruitment. Participants will be engaged in the study for up to 210 days (7 months), which will include 180 days (6 months) of active intervention (PILOT) or TAU, and a 210-day follow-up assessment after the completion of the intervention.

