10. Increase in Recovery Capital Score: A participant will have achieved Step 10 if the total score on the Assessment of Recovery Capital (ARC form) scale (Groshkova, et al.; range 0-50) increases by a value equivalent to 0.5 standard deviations within the validation sample score of 11.54 (Ward, et al.) from baseline to the 30- 90- OR 180-day visit. This equates to a 5.77 or greater point increase. A response of “agree” counts as one point. A participant will be counted as having met Step 10 if they increase above the baseline score at ANY study visit even if there is/was a decrease in ARC at previous or subsequent study visits.

If the algorithm is unclear regarding whether a specific step was achieved post-randomization, it will be adjudicated by an independent committee at the end of the trial. Should it be unclear if a specific step was achieved, the following dispute resolution will be employed. A Dispute Resolution Panel will be formed that includes 3 members. One member will be selected by the NIDA CCTN, one member will be selected by the lead team, and those two members will select a third that is independent and a context expert in opioid-related overdose. That 3-member committee will then be asked to determine if the step is met based on the definition above.

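### Exploratory Aim 1 covers how much recovery capital changes, but the ARC score is compared between arms only as a yes/no step

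*SAP*

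**What the plan says.** SAP 2.1 states the exploratory objective as to "assess the effects of PILOT versus TAU on the magnitude of achievement on the modified SUD Cascade of Care". SAP 7.7 words Aim 1 as both reaching a step and the "magnitude of achievement (e.g., improvement in Addiction Recovery Capital Scale by 3 points, number of steps achieved"). Protocol 5.4 and 7.3 carry the same aim.

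The method is in SAP 7.8 item 1: "Each step on the modified SUD Cascade of Care will be treated as a binary outcome". A separate logistic regression gives an odds ratio per step, repeated for Days 30, 90 and 180. Protocol 14.8 item 1 matches it.

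ARC enters the efficacy analyses through Step 10 (SAP 7.4.1). That step asks for a rise of "0.5 standard deviations within the validation sample score of 11.54", and the SAP adds: "This equates to a 5.77 or greater point increase". It can be met at any of the three treatment-period visits, and missing step data count as not met. SAP 7.8 also says that "the actual analysis methods may differ from the proposed methods given below".

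**The concern.** The aim has two parts, and one of them has only half a method. Of the two examples given for magnitude, the step count is analysed as a secondary outcome (SAP 7.5.1). ARC improvement has no analysis on its own scale, although the assessment schedule (Protocol 11.2) collects it at baseline and at Days 30, 90, 180 and 210.

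A yes/no step cannot show how far recovery capital moved. A participant who gains 3 points, the size Aim 1 names, scores the same on Step 10 as one who gains nothing. One who gains 6 scores the same as one who gains 20. The trial would report an odds ratio at one cut and no estimated mean difference for ARC. Depending on how the effect develops over time, it could also give up power on that scale.

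**Working it through.** **Inputs from the documents.** Sample size: "A total of approximately 150 eligible patients will be randomized (approximately 50 per each of 3 sites) in a 1:1 ratio", so 75 per arm. Testing: "two-sided tests and with a type I error rate of 0.05". ARC range 0-50, one point per item agreed with (SAP 7.4.1). SD 11.54; Protocol 7.2.1 makes clear that this is the validation sample's SD.

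**Assumed, because the documents give none.** True effect 3 or 5.77 points; between-visit correlation *r* 0.5-0.7; baseline mean 25 or 35; missingness 0 or 25% per visit.

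**1. The plan's own figure.** 0.5 × 11.54 = 5.77, so the cut reproduces. The 3-point example is 3/11.54 = 0.26 SD and lies below it. As scores are whole points, Step 10 in effect needs a rise of 6. The last sentence of the Step 10 definition restates the rule as any rise above baseline, which does not match the 5.77-point rule. The documents give no power figure for Aim 1.

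**2. Where ARC is used.**

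| Part of Aim 1 | Analysis |
|---|---|
| Each step reached or not | Logistic model per step, SAP 7.8 item 1 |
| Number of steps | Poisson count model, SAP 7.5.1; by SUD group, SAP 7.6 |
| ARC change | None on the 0-50 scale; only Step 10 as yes/no |

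No SAP section or table shell compares ARC totals after baseline by arm.

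**3. One visit, *r* = 0.5, no change in the control arm, true effect 5.77 points.**

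- Yes/no: SD of change = 11.54 × √(2 × (1 − 0.5)) = 11.54. Control proportion = 1 − Φ(5.77/11.54) = 1 − Φ(0.5) = 0.31. PILOT proportion = 1 − Φ(0) = 0.50. Power with 75 per arm is 67%.
- Change score: SE = 11.54 × √(2/75) = 1.884; 5.77/1.884 = 3.06; power = Φ(3.06 − 1.96) = 87%.
- Baseline-adjusted: SD = 11.54 × √(1 − 0.5²) = 9.99; SE = 9.99 × √(2/75) = 1.632; 5.77/1.632 = 3.54; power = Φ(3.54 − 1.96) = 94%.

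For 80% power these need 102, 63 and 48 per arm. For a true effect of 3 points the powers are 23%, 36% and 45%. Over a grid with *r* 0.3-0.7, control drift 0-6 points and effects of 3, 4 or 5.77 points, the yes/no step has relative efficiency 0.58-0.63 against the change score and 0.40-0.54 against the adjusted score.

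**4. The actual any-visit rule, by simulation.** Baseline plus three visits, normal scores with SD 11.54 and equal correlations, rounded and held to 0-50. A two-proportion test of Step 10 is set against analysis of covariance of Day 180 ARC on baseline. No missing data:

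| True effect at Days 30/90/180 | Any-visit Step 10 | Day 180, baseline-adjusted |
|---|---|---|
| 3/3/3 | 21-43% | 43-59% |
| 5.77/5.77/5.77 | 52-92% | 92-99% |
| 6/4/2 | 34-71% | 23-31% |
| 6/3/0 | 24-56% | 4-7% |

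With a constant effect and 25% missing independently per visit, scored as not met for the step, the full-scale analysis gains about 3-29 points of power. Monte Carlo error is a point or two.

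**The case against.** The strongest reply is that the aim is exploratory and its methods are explicitly left open. SAP 1.0 assigns SAP 7.8 to the Lead Node and claims completeness only for primary, secondary and safety outcomes. Protocol 14.1.1 restates this objective as achievement of each step, which the logistic models do address. The 3-point ARC example is itself worded like a cut-off. All of this stands and limits the weight of the point. It does not supply a method for a part of the aim that SAP 2.1 and 7.7 still state, and choosing one after seeing the data is weaker than writing it now.

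The any-visit rule also has a rationale: Protocol 6.2 expects early responders and participants who disengage and return. The last two rows of the simulation table show that a Day 180 comparison alone can then do worse than the step. That objection stands too, and it is why each visit should be reported.

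A reader might go further in three ways that the documents do not support:

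- *That magnitude is not analysed at all.* The step count is modelled in SAP 7.5.1 and summarised in SAP Table 35.
- *That DSM-5 criterion counts are an equal omission.* Aim 1 does not name them. A primary-SUD count is undefined for enrolled participants with no SUD at baseline. The power loss from Step 8, with every input assumed, ran from about 0 to 54 points.
- *That planning of the larger trial is undermined.* The markers listed for sizing it in Protocol 7.4 (Milestone 3) are repeat overdose, mortality, MOUD initiation and overdose risk behaviors. ARC is not among them.

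**Conclusion.** The point holds for ARC. As written, the plan leaves the ARC part of Aim 1 without an estimate of magnitude. With an effect constant over visits, the yes/no step has clearly less power than a baseline-adjusted comparison: about 21-43% against 43-59% for 3 points, and 52-92% against 92-99% for 5.77 points. These figures rest on a validation-sample SD and on assumed effects, correlations and baseline means.

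It would be tempting to say that most of the information is lost. The single-visit efficiencies put the loss at about 40% against a change score and about half or somewhat more against an adjusted score, and under a fading effect the any-visit step has more power than Day 180 alone. The firm finding is the missing estimate; the loss of power depends on the scenario. This is an inexpensive improvement to an exploratory aim, and no primary, secondary or safety conclusion depends on it.

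**What to change.** Add to SAP 7.8 item 1 and Protocol 14.8 item 1:

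> In the ITT population, ARC total score at Days 30, 90 and 180 will be compared by a linear mixed model with baseline ARC, treatment, day, treatment × day, site and homelessness stratum, reporting the mean difference and 95% CI at each visit.

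Keep the per-step odds ratios as the yes/no part of the aim. Reconcile the 3-point example in Aim 1 with the 5.77-point cut of Step 10, and align the closing sentence of the Step 10 definition with that cut. A model for the DSM-5 criterion count is optional; if added, restrict it to participants with a primary SUD at baseline.

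The cost is wording and one model on data already collected. The downside is one more unadjusted exploratory analysis, in a set for which the SAP already makes no multiplicity adjustment.

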8.0 STUDY POPULATION

A total of approximately 150 eligible individuals in the ED who have been identified as having experienced a NFOO in the past 30 days will be randomized (approximately 50 per each of 3 sites). Study staff will confirm self-reported overdose with the participant, and those who confirm an NFOO meeting the criteria below will be eligible. Those who are initiated on MOUD in the ED will be included. Randomized participants will be stratified by study site and homelessness status.

Non-Fatal Overdose Involving Opioids (NFOO) Description:

A person will be considered to have experienced a NFOO if he/she/they self-report affirmatively:

1. Do you think you may have experienced an overdose?

AND

2. Do you think that overdose may have involved opioids (heroin, fentanyl, or prescription pain medications such as morphine, oxycodone, or hydrocodone)?

Those who are considered to have experienced a NFOO according to answers to the questions above will be eligible for the study if the self-reported NFOO occurred in the past 30 days and other inclusion criteria are met. An overdose does not need to be confirmed for the participant to be included but should be self-reported as an overdose involving opioids by the patient to be eligible for study procedures. Alternative definitions for an overdose were considered; however, it was decided that this definition will appropriately identify the desired population for inclusion. In addition, the definition is consistent with current practice to identify OD survivors. Patients may be in the ED for an overdose event or for another SUD-related event if the NFOO occurred in the past 30 days.

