Excluding active suicidality and intentional/suicidal overdose attempts at screening: Because most overdose deaths involving opioids are accidental [36], and because managing an individual immediately after an intentional overdose is outside the scope of standard peer support service practices, individuals reporting that the Index NFOO was intentional, as well as those who are actively suicidal, will be excluded. Any participant who scores >0 (“not at all”) on question 9 of the Patient Health Questionnaire-9 (PHQ-9; “Over the last 2 weeks, how often have you been bothered by any of the following problems? Thoughts that you would be better off dead or of hurting yourself in some way?”) will have their suicidal ideation assessed by a medical clinician. Those with active suicidal ideation will be managed by the Emergency Department per standard care but will not be enrolled in the study. Those with “passive” suicidal ideation, defined as hopelessness and/or passive wish for or indifference about death, without current suicide plan or intention, will be eligible, as these symptoms are relatively common in those with active SUD.

Including those admitted to the hospital from the Emergency Department: Those admitted to the hospital from the ED but otherwise able to complete study procedures will be included (if able to meet other inclusion criteria), as it is the current practice of FORCE CPSSs to follow participants during hospitalization and after hospital discharge.

Including those discharged from the ED before screening can be completed: Some individuals may be identified as potential candidates for the study, but either leave Against Medical Advice (AMA) or are discharged from the ED before screening can be completed. If study staff are able, with verbal consent, to contact identified individuals with a NFOO within 72 hours of ED discharge, they can be screened for entry into the study and can be enrolled within one week of the ED discharge.

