10.0 STUDY PROCEDURES

10.1 Screening

Patients will be recruited at each ED site, either in-person or via remote techniques (if needed). Study sites will operate under the MUSC policies and procedures for recruitment given the SmartIRB master reliance agreement. As such, recruitment procedures will be the same across study sites, with any differences outside of the MUSC policies being specifically stated and approved as part of local study site standard operating procedures (SOPs). Research staff will work during times to include evenings and weekends to ensure success with enrollment. Research staff will identify patients seen in the ED by screening, reviewing the EHR trackboards and by provider or TAU peer referral. Research staff will keep a log of all patients approached and the outcome of that approach (Screening and Approach Log). Potential participants identified will be evaluated by a member of the research staff for eligibility.

Patients will be stabilized per ED usual care and receive TAU per that ED site, noting that each site will have an operationalized peer support specialist system already in place in the ED which may be a part of TAU (**Figure 1**). After clinical stabilization and TAU, research staff will ask for verbal consent to complete screening forms and assessments, which will include questions about overdoses in the past 30 days, reason for the ED visit, and other items that may exclude that individual from study inclusion. Research staff will follow an approved verbal consent script which details how their information might be used/exceptions to confidentiality based on urgent medical concerns during the screening process.

Patients who appear to be eligible will then be asked about interest in the study. If the answer is yes, research staff will describe the study and if the participant remains interested and would like to continue, written informed consent will begin.

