11.2 Table 1: Table of Assessments/Forms

Assessment	Time Needed to Complete (only for ppt assessments)	Screening	Random- ization	Baseline	Day 30	Day 90	Day 180	Day 210	As Needed
		(Index ED Visit/Enrollment) – Virtual or In-person			Phone, Virtual, or In- person	Phone, Virtual, or In- person	Phone, Virtual, or In- person	Phone, Virtual, or In- person	
Screening									
Screening Enrollment Form	5 mins	X							
Prisoner Status Assessment	2 mins	X							
Demographics	5 min	X							
Patient Health Questionnaire-9	2 mins	X			X	X	X	X	
Screening Exit Survey	10 mins	X							
Written Informed Consent	30-45 mins	X							
Inclusion/Randomization and Study Visits									
Study Enrollment Form			X						
Visit Documentation				X	X	X	X	X	
Locator Information Form	5-10 mins			X	[X]	[X]	[X]	[X]	
Overdose Information	3 mins			X	X	X	X	X	
Urine Drug Test	5 mins			X	X	X	X	X	
Overdose Risk Behavior Checklist	3 mins			X	X	X	X	X	
Harm Reduction Checklist	3 mins			X	X	X	X	X	
Step 2-7 Assessment Form (SAF 2-7)	4 mins			X	X	X	X	X	

Assessment	Time Needed to Complete (only for ppt assessments)	Screening	Random- ization	Baseline	Day 30	Day 90	Day 180	Day 210	As Needed
		(Index ED Visit/Enrollment) – Virtual or In-person			Phone, Virtual, or In-person				
MOUD Confirmation Assessment (confirmed via objective measures)	3 mins				X	X	X	X	
MOUD Current Status	2 mins			X	X	X	X	X	
Readiness Ruler	1 min			X	X	X	X	X	
Alcohol and Substance Use History (PhenX Tier 1)	10 mins			X					
Timeline Follow-Back (7 day)	3 mins			X	X	X	X	X	
DSM-5 Checklist	5-10 mins			X	X	X	X	X	
ED MOUD Administration (obtained from EMR)				X					
End of Treatment							X		X
Assessment of Recovery Capital	8 mins			X	X	X	X	X	
Chronic Pain History	1 min			X					
Tobacco Use History	2 mins			X					
Fagerstrom Test for Nicotine Dependence	2 mins			X					
Cannabis Use Assessment	1 min			X			X	X	
Quality of Life	3 mins			X	X	X	X	X	
Crime and Criminal Justice	3 mins			X	X	X	X	X	
Treatment Satisfaction Form	5 mins							X	X
Administration or Non-Visit Based Forms									
Mental Health Follow-up Assessment	2 mins								X
ED Visits and Hospitalizations	5 mins								X
Screening Approach	1 min								X
Contact Log	5 mins								X
Death Form	5 mins								X
Protocol Deviation and Review Forms	5 mins								X
Study Completion Form	2 mins							X	X
Inventory – Supplies Form	5 mins								X
TAU Characterization Form	15-20 mins								X
Peer Characterization Survey	5-10 mins								X
Remote Assessments									

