11.4.7 ED MOUD

This form will record information regarding medications for OUD administered during the index ED admission, according to patient self-report at the time of ED discharge, including medication name (methadone, SL buprenorphine, SL buprenorphine/naloxone, oral naltrexone, and extended-release naltrexone), date, and total dose administered (if known). This data will be used to determine MOUD exposure in the ED Index visit.

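### Exploratory Aim 2 does not tie MOUD initiation in the ED to the time of randomization, so outcomes already settled at assignment can dilute the PILOT-versus-TAU odds ratio

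*SAP*

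**What the plan says.** **Aim and analysis.** SAP 7.7 states Aim 2 as: "To evaluate the effectiveness of PILOT versus TAU on initiation of MOUD in the ED (EDM) for those with any level of OUD at baseline". SAP 7.8 item 2 analyses it thus: "Initiation for medications for OUD in the ED, among those participants with OUD, will be summarized by frequencies and percentages in each treatment arm". An odds ratio with 95% confidence interval and a chi-squared test follow, and the odds ratio is labelled the effect of PILOT. On testing, SAP 7.8 adds: "The exploratory objectives will be tested as applicable, with two-sided tests and with a type I error rate of 0.05". Protocol 5.4, 7.3 and 14.8 carry the same aim and analysis. None of these sections limits the outcome to MOUD started after randomization, or the population to people still in the ED when randomized.

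**Data source.** Protocol 11.4.7 describes the form: "This form will record information regarding medications for OUD administered during the index ED admission, according to patient self-report at the time of ED discharge". It lists medication name, date and total dose, and mentions no time of day. Table 1 in Protocol 11.2 marks the same form as obtained from the electronic medical record (EMR). SAP 7.7 says self-report.

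**Order of events.** Protocol 10.1 says: "After clinical stabilization and TAU, research staff will ask for verbal consent to complete screening forms and assessments". Protocol 10.5 defines TAU to include MOUD where indicated and available. Protocol 8.0, repeated in SAP 2.3, says: "Those who are initiated on MOUD in the ED will be included". For patients who leave the ED before screening is complete and can be contacted within 72 hours, Protocol 8.3 says "they can be screened for entry into the study and can be enrolled within one week of the ED discharge". Protocol 6.1 also allows remote screening and consent after discharge. Protocol 8.4.1.3 allows community recruits whose overdose, with transport or admission to an ED, was in the past 30 days.

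**The concern.** A randomized comparison measures an effect only on what can still happen after assignment. Aim 2 is set up to measure MOUD over the whole index ED admission, and that window opens before randomization for everyone. For people enrolled after discharge it has also closed.

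Two groups therefore enter the odds ratio with a value that PILOT cannot alter. Those given MOUD in the ED before randomization count as initiated in either arm. Those randomized after leaving the ED keep whatever status they left with.

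The practical risk is a false impression of no effect. The trial is meant to inform a larger one, and an odds ratio close to 1 could be read as PILOT having no influence on ED initiation when part of the shrinkage comes from including settled outcomes.

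**Working it through.** **No planned figure to reproduce.** The documents give no rate, effect size or power for Aim 2. The check is of the sequence of events, followed by an illustration on assumed rates.

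**Sequence.** Stabilization and TAU (which may include MOUD) come first, then verbal consent and screening (Protocol 10.1), written consent (10.2), eligibility confirmation (10.3) and randomization (10.4). At randomization an OUD participant is in one of three states:

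1. in the index ED with no MOUD yet: outcome open;
2. already given MOUD during the visit: settled as yes;
3. out of the ED: settled as yes or no.

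The plan pools all three.

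**Illustration A: effect on the odds ratio.** Let *f* be the share of OUD participants given MOUD before randomization, *e* the share of the remainder enrolled after discharge, and *p* the initiation rate among those still open. Assume *p* = 20% in PILOT and 10% in TAU. The planned analysis sees

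observed rate = f + (1 − f)(1 − e)p.

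With f = 0 and e = 0, OR = (0.20/0.80)/(0.10/0.90) = 2.25. With f = 0.10 and e = 0:

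- PILOT: 0.10 + 0.90 × 0.20 = 0.28
- TAU: 0.10 + 0.90 × 0.10 = 0.19
- OR = (0.28/0.72)/(0.19/0.81) = 1.66

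| f | e | PILOT | TAU | OR | Difference (points) |
|---|---|---|---|---|---|
| 0 | 0 | 20% | 10% | 2.25 | 10 |
| 0.10 | 0 | 28% | 19% | 1.66 | 9 |
| 0.20 | 0 | 36% | 28% | 1.45 | 8 |
| 0.30 | 0 | 44% | 37% | 1.34 | 7 |
| 0.10 | 0.30 | 22.6% | 16.3% | 1.50 | 6.3 |
| 0.20 | 0.30 | 31.2% | 25.6% | 1.32 | 5.6 |
| 0.30 | 0.30 | 39.8% | 34.9% | 1.23 | 4.9 |

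The absolute difference shrinks by the factor (1 − f)(1 − e). The odds ratio, which is the planned measure, shrinks faster when many of the settled outcomes are yes.

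**Illustration B: effect on power.** Here *f* is the share settled for either reason and *g* the share of those who had received MOUD, so the observed rate is fg + (1 − f)p. Assume p = 40% in PILOT and 20% in TAU, two-sided alpha 0.05, and 75 per arm (all 150 participants have OUD, the most favourable case).

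| f | OR (g = 1 / 0.5 / 0) | Power (g = 1 / 0.5 / 0) |
|---|---|---|
| 0 | 2.67 | 77% |
| 0.25 | 1.83 / 1.95 / 2.43 | 45% / 49% / 60% |
| 0.50 | 1.56 / 1.52 / 2.25 | 25% / 24% / 40% |
| 0.75 | 1.42 / 1.22 / 2.11 | 12% / 9% / 21% |

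At f = 0.50 a comparison restricted to open outcomes keeps about 75 × 0.5 ≈ 37 per arm and has 47% power at 20% versus 40%. The unrestricted analysis of all 75 per arm has 24% to 40%. On these assumptions the smaller group gives the more powerful test.

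**The case against.** **Care continues after assignment.** Protocol 6.1 says participants continue TAU after randomization, Protocol 10.5 has TAU care running until ED discharge or transfer, and Protocol 2.4 and 6.1 have PILOT beginning in the ED. MOUD can therefore be started there after randomization. This stands. A reader might infer that much of the outcome is fixed beforehand, but no section gives the share. Protocol 8.4 makes the ED the primary place of recruitment, Protocol 8.3 applies post-discharge enrolment to some individuals, and community recruitment is a contingency.

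**Randomization balances earlier MOUD.** This also stands. A reader might conclude that the comparison is biased, that a chance imbalance would create a spurious finding, or that the aim cannot be answered at all. The documents do not support that. The arms are comparable in expectation, and the test and interval already allow for chance differences. The analysis remains valid for the difference in total ED MOUD. What it loses is sensitivity to anything PILOT does.

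**Dates may suffice.** They separate some cases: presentation can be up to 48 hours earlier (Protocol 8.1) and enrolment up to a week after discharge. The case report form itself is not shown, so the lack of a clock time is inferred from its description. The MOUD Current Status form (Protocol 11.4.4) records the date of the last dose but, under SAP 3.2.4, some baseline assessments may follow randomization. Dates will not always order two events in one visit.

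**It is exploratory.** SAP 7.8 lets methods change, and SAP Table 1 gives these analyses to the Lead Node. That limits the severity. It does not supply the missing definition.

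**Conclusion.** The point holds as one of definition and dilution. As written, Aim 2 counts MOUD given before assignment, and the settled status of people who had left the ED, in a contrast labelled the effect of PILOT. The result is an odds ratio pulled toward 1 and lower power, without systematic bias or type I error inflation.

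The size depends on shares and rates that the documents do not give; every rate in the illustrations is assumed. They also presume that MOUD is available in the ED. Protocol 9.3 lets all three sites offer it or none offer it, and if none did, the outcome would be near zero in both arms.

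The conflict over the form's source, self-report or EMR, is real and separate. Severity is minor: no primary, secondary or safety conclusion rests on this aim.

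**What to change.** In SAP 7.7 and 7.8 item 2, and in Protocol 14.8 item 2:

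- Restrict the PILOT-versus-TAU comparison to participants with baseline OUD who were still in the index ED at randomization and had received no MOUD during that visit before randomization. The limit should be the ED and not the hospital, because the endpoint is ED initiation and admitted patients may already have left the ED.
- Count only a first ED dose given after randomization.
- Report ED MOUD given before randomization by arm as a baseline characteristic.
- Order the events by the EMR administration time and the randomization timestamp.
- Reconcile the source of the ED MOUD form between Protocol 11.4.7 and SAP 7.7 (self-report) and Protocol Table 1 (EMR).

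Both added restrictions use facts fixed at randomization, so the randomized comparison is preserved. The cost is revised wording, a brief EMR time lookup per participant and a smaller denominator. Nothing in clinical care changes.
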